4.1 ANALYSIS POPULATIONS

4.1.1 Intent-to-Treat Population

All randomized patients will be included in the Intent-to-Treat (ITT) Population. Patients who prematurely withdraw from the study for any reason and for whom an assessment is not performed for whatever reason will still be included in the ITT analysis. Patients who receive an incorrect medication or vaccination rather than the one they are assigned to will be summarized according to their randomized treatment group.

In the event that at least 1 randomized patient withdraws from the study before the end of the ISP, then tabular summaries of baseline characteristics only will be presented for the ITT Population. If all randomized patients complete the ISP, then no summaries/analyses will be presented for ITT Population.

4.1.2 Observed Cases Population

The Observed Cases (OC) Population is defined as all randomized patients who complete the ISP. Patients who receive an incorrect medication or vaccination rather than the one that they are assigned to will be summarized according to their randomized treatment group.

All immunization outcome measures will be analyzed using the OC Population.

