3.3.2.1 Tetanus Toxoid Adsorbed Vaccine

TT vaccine will be administered as a combined adsorbed vaccine with diphtheria (tetanus-diphtheria [Td] or diphtheria and tetanus toxoid [DT]) or with diphtheria and acellular pertussis (diphtheria-tetanus-acellular pertussis [DTaP] or tetanus-diphtheria-acellular pertussis [Tdap]).

Group A (active) patients will receive a TT-containing vaccine 12 weeks after the first OCR administration. Serum anti-tetanus titers will be measured 4 and 8 weeks after vaccine administration and compared with levels immediately prior to vaccine administration.

Group B (control) patients will not receive OCR during the Immunization Study Period. They will receive a TT-containing vaccine at Day 1/Week 1. Serum anti-tetanus titers will be measured 4 and 8 weeks after vaccine administration (Day 28/Week 4 and

Day 56/Week 8) and will be compared with levels immediately prior to vaccine administration.

3.3.2.2 23-Valent Pneumococcal Polysaccharide Vaccine

The 23-PPV will be administered to Group A (active) patients 16 weeks after the first OCR administration. Serum titers against all 23 serotypes (1, 2, 3, 4, 5, 6b, 7F, 8, 9N, 9V, 10A, 11A, 12F, 14, 15B, 17F, 18C, 19F, 19A, 20, 22F, 23F and 33F) will be measured 4 and 8 weeks after vaccine administration and will be compared with levels immediately prior to vaccine administration.

Group B patients will receive the 23-PPV vaccine at Day 28/Week 4. Serum titers will be measured 4 and 8 weeks after vaccine administration and will be compared with levels immediately prior to vaccine administration.

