4.4 OUTCOME ANALYSIS

No hypothesis testing will be performed.

For immunology endpoints, pre-immunization levels are those obtained immediately prior to administration of a vaccine.

Patients with missing immunology assessment data will not be included in the calculations. No missing data imputation methods will be applied.

For immunology endpoints, except where stated, tabular presentations will show Group A (Groups A1 and A2 combined) and Group B.

Summaries will be presented for the OC Population only.

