Group A1: Patients in Group A1 receive the 23-PPV vaccine at Week 16 and also the 13-PCV booster vaccination 4 weeks later at Week 20. All 23 serotypes are assessed immediately prior to 23-PPV vaccination at Week 16, again prior to the 13-PCV “booster” 4 weeks later at Week 20, and then again 4 weeks after that at Week 24.

Group A2: Patients in Group A2 receive the 23-PPV vaccine at Week 16, but do not receive the 13-PCV “booster”. All 23 serotypes are assessed immediately prior to 23-PPV vaccination at Week 16, again 4 weeks later at Week 20 and again 4 weeks after that at Week 24.

Group B: Patients in Group B follow a similar schedule to Group A2, but earlier in the study. They receive the 23-PPV vaccine at Week 4, and do not receive the 13-PCV “booster”. All 23 serotypes are assessed immediately prior to 23-PPV vaccination at Week 4, again 4 weeks later at Week 8 and again 4 weeks after that at Week 12.

Summaries will show the following groups separately: Group A1, Group A2, Group A (Groups A1 and A2 combined), and Group B. Pairwise between-group comparisons will show:

- Group A1 versus Group A2
- Group A1 versus Group B
- Group A2 versus Group B
- Group A (A1 and A2 combined) versus Group B

Note that the first 3 of the 4 comparisons above, which involve treatment groups A1 and A2 separately, should be interpreted with some caution, since patients were not assigned to these 2 treatment groups randomly (patients were randomized to Group A or

Group B, and within Group A were non-randomly assigned to Group A1 or A2, based on seasonality considerations).

A positive response against a serotype is defined as developing either a 2-fold increase in level or a > 1 $\mu\text{g/mL}$ rise in level, compared with pre-immunization levels.

At 4 weeks after the 23-PPV vaccine, the number and proportion of patients in Groups A1, A2, A (A1 and A2 combined), and B with a positive response (as defined above) against each of the 23 serotypes will be presented. For the same 4 pairwise between-group comparisons described earlier in this section, pairwise between-group differences in positive response rates and the associated 95% CI will also be presented for each serotype, using a normal approximation method.

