4.4.5 Sensitivity Analyses

If there are any reported major protocol deviations relating to, or other issues reported which may affect data quality or analysis interpretability for a specific primary or secondary immunology endpoint, then as sensitivity analyses, the summaries and analyses specified above for that specific endpoint may be repeated excluding those patients with major protocol deviations/other issues.

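### The completers-only population would discard observed tetanus titers, including primary-endpoint ones, from anyone who leaves after the reading but before the last Immunization Study Period visit; the expected effect is small

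*SAP*

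**What the plan says.** SAP 4.1.2 sets the population: "The Observed Cases (OC) Population is defined as all randomized patients who complete the ISP". It then applies that population to every immunization endpoint: "All immunization outcome measures will be analyzed using the OC Population". SAP 4.4 repeats the restriction ("Summaries will be presented for the OC Population only") and separately handles missing titers: "Patients with missing immunology assessment data will not be included in the calculations".

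Two other parts of the SAP might have brought early leavers back, and neither does. Under SAP 4.1.1, if anyone withdraws during the ISP, "tabular summaries of baseline characteristics only will be presented for the ITT Population". Under SAP 4.4.5, analyses "may be repeated excluding those patients with major protocol deviations/other issues", which is optional and only removes more patients.

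On timing, Protocol 3.1 ends the ISP at Day 169/Week 24 for Group A and Day 84/Week 12 for Group B. Protocol 4.4.2.1 gives the TT vaccine at Day 85 (A) or Day 1 (B). Protocol 3.3.2.1 says of both groups that "Serum anti-tetanus titers will be measured 4 and 8 weeks after vaccine administration".

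**The concern.** Completing the ISP happens after randomization and, for several endpoints, after the endpoint itself has been read. It has no bearing on whether an earlier titer is valid. A patient who attends at Day 140 (A) or Day 56 (B), has an assayed primary result and then leaves is excluded from the primary analysis.

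A versus B is the only randomized comparison in the trial; the SAP itself advises caution for A1 and A2 comparisons because that split was not random. Conditioning A versus B on later completion adds selection that could be avoided. Its direction cannot be known in advance: the trial is open-label and only Group A receives ocrelizumab in the ISP, so reasons for leaving may differ between groups. The disposition tables in SAP 4.2 will show how many left and why, but not how they responded.

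The rule also sits uneasily with Protocol 4.8.2, under which results already obtained from samples before withdrawal are to be used. That passage is about sample handling and also has untested routine samples destroyed on withdrawal from the study, so it is a tension rather than a contradiction.

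**Working it through.** **Which endpoints are exposed** (visit days from Protocol Appendix 1, Tables A and B)

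| Endpoint | Group A | Group B | Before last ISP visit? |
|---|---|---|---|
| 4-week TT, 4-week KLH | Day 112 | Day 28 | Yes, about 8 weeks |
| 8-week TT (primary), 4-week 23-PPV, 8-week KLH | Day 140 | Day 56 | Yes, about 4 weeks |
| Influenza, 4 weeks after vaccine (A2 and B) | varies | varies | Yes, if vaccinated early |
| 8-week 23-PPV, 12-week KLH | Day 169 | Day 84 | No |

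SAP 4.4.2.2 gives the same pattern for 23-PPV in Group A2, where serotypes are assessed before vaccination, "again 4 weeks later at Week 20 and again 4 weeks after that at Week 24". The Week 20 reading is exposed and the Week 24 reading is not.

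**The plan's own precision figure.** SAP 2.3 states a half-width of 0.201 at 70% versus 70% with about 100 patients, 2:1. The formula is 1.96 × √[0.7 × 0.3 × (1/nA + 1/nB)].

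- 67 and 33 patients: 0.191.
- 60 and 30 patients: 0.2008.

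The stated figure therefore matches 90 evaluable patients, which would fit an unstated 10% loss. That is an inference; neither document states a dropout rate.

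**Expected number of discarded primary titers.** Assumption: constant dropout of d = 2%, 5% or 10% per 12 weeks, with 67 and 33 randomized. The daily hazard is h = −ln(1 − d)/84 and S(t) = exp(−h·t), with t in days since Day 1.

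- Group A: 67 × [S(139) − S(168)] = 0.45, 1.08, 2.01.
- Group B: 33 × [S(55) − S(83)] = 0.22, 0.54, 1.06.
- Total: 0.67, 1.62, 3.07.
- As a share of randomized patients: A 0.7%, 1.6%, 3.0%; B 0.7%, 1.6%, 3.2%.
- Chance of at least one, 1 − (1 − pA)^67 × (1 − pB)^33, where pA and pB are the bracketed differences: 49%, 80%, 96%.

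With the hazard halved after the titer visit, the totals are 0.34, 0.81 and 1.55, and the chances 29%, 56% and 79%.

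**4-week TT endpoint.** 67 × [S(111) − S(168)] + 33 × [S(27) − S(83)] = 1.33, 3.23, 6.19.

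**Effect on precision** (half-width, all available primary titers versus completers)

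| d per 12 weeks | Available titers | Completers |
|---|---|---|
| 2% | 0.1929 | 0.1936 |
| 5% | 0.1959 | 0.1976 |
| 10% | 0.2013 | 0.2049 |

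**Effect on the estimate.** Start from 70% in both groups with 67 and 33 titers. Dropping k non-responders changes that group's rate by 0.7n/(n − k) − 0.7. Dropping one responder changes it by (0.7n − 1)/(n − 1) − 0.7.

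| Discarded | Change in A minus B (points) |
|---|---|
| One non-responder in B | −2.2 |
| One non-responder in A | +1.1 |
| Two non-responders in A | +2.2 |
| One responder in B | +0.9 |
| One responder in A | −0.5 |

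**A different dropout assumption.** Taking 2% to 20% loss per group over the whole ISP instead, 0.4 to 4.1 primary titers are discarded in total and the half-width grows by 0.001 to 0.007. At 10% loss it is about 1.1 titers in each group, with the half-width going from 0.198 to 0.201.

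**The case against.** The strongest reply is that the harm is conditional and small. Nothing is lost unless someone leaves in a window of about four weeks, and every count above rests on an assumed dropout rate. The window is almost equal in the two groups (29 and 28 days), so it does not by itself favour either. The trial is descriptive, with no hypothesis test, so no error rate is at stake. A completer set also keeps largely the same patients across the serial TT, 23-PPV and KLH readings, which is a recognisable convention, although the SAP does not give that reason.

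Most of this stands, and it is why the point is minor. The counts are expectations, not bounds: actual numbers could be higher if withdrawals cluster late. They could also be lower, because some samples may be untested and destroyed at withdrawal, and because only ISP completers may enter the extension (Protocol 4.1.3), which gives patients a reason to stay. The 10% scenario implies about 16 of 100 patients lost during the ISP and should carry less weight than the 5% scenario, which implies about 8 and is nearer the loss that the stated half-width would fit. The Protocol 4.8.2 argument is supporting only.

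None of this gives a reason to discard a valid titer. A common patient set across readings can still be shown through a completer sensitivity analysis.

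**Conclusion.** The concern holds, as a minor one. For endpoints read before the last ISP visit, including the primary, the completion rule can only remove patients who have the result, and nothing in the SAP brings them back. That part follows from the text.

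The size depends on the assumed dropout: about one to three primary titers in 100 patients over the range used, fewer if late dropout is lower, and none if nobody leaves late. The likely shift in A minus B is a point or two, within a half-width of about 20 points. The 4-week TT endpoint is more exposed, at about twice as many titers. The 8-week 23-PPV and 12-week KLH readings are essentially unaffected.

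**What to change.** In SAP 4.1.2 and 4.4, define the population endpoint by endpoint: all randomized patients, in the group to which they were randomized, who received the relevant vaccine and have both the pre-vaccination and the endpoint-visit titer, whether or not they complete the ISP. Keep ISP completers as a sensitivity analysis.

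This does not recover patients who leave before the titer, and they should not be scored as non-responders instead. Group A waits 20 weeks for its primary reading and Group B waits 8, so at an equal 70% response that scoring alone would give A minus B of 0.7 × [S(139) − S(55)] = −1.4, −3.4 or −6.5 points in the three dropout scenarios.

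The cost is SAP wording and one population flag per endpoint. The completer tables already planned become the sensitivity analysis, and no extra data are needed.

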4.1.3 Safety Population

The Safety Population will include all patients who received any ocrelizumab or any vaccine. Randomized patients who received an incorrect medication or vaccine rather than the one they were assigned to will be summarized in the group according to the medication or vaccine actually received.

All safety outcome measures will be analyzed using the Safety Population.

4.2 ANALYSIS OF STUDY CONDUCT

All data up to the point of the CCOD will be included to evaluate study conduct. This will include complete data from the ISP and any data from the OOE and SFU Periods available at the CCOD.

The following analyses will be performed to evaluate the study conduct:

- Summary of enrollment by country and center (numbers and percentages of patients enrolled, presented by treatment group)
 - Summaries of randomized patients, of the ITT Population if any summaries are produced for this population, and of the OC and Safety Populations (numbers and percentages of patients in each population, presented by treatment group)
- Summary of patient disposition for the ISP and OOE and SFU Periods (at each visit/during each study period, numbers and percentages of patients completing, discontinuing and ongoing, presented by treatment group)
- Summary of reasons for patients discontinuing during the following study periods (numbers and percentages of patients discontinuing for each reason within each period, presented by treatment group):

ISP

SFU Period after the ISP (these patients did not enter the OOE)

OOE

SFU Period after completing the OOE

Study as a whole

A listing of reasons for all patient discontinuations from the study will also be provided.

- Listing of key eligibility criteria violations and other major protocol deviations

4.3 ANALYSIS OF TREATMENT GROUP COMPARABILITY

For continuous variables, the mean, median, SD, minimum and maximum will be presented for each treatment group. For categorical variables, number and percentage of patients in each category will be presented for each treatment group.

Except where stated, all assessments of treatment group comparability will utilize the date of the baseline visit (not the date of the screening visit) as the reference point in time.

Except where stated, summary tables will be presented for both OC and Safety Populations. In the event that at least one randomized patient withdraws from the study before the end of the ISP, then tabular summaries of baseline characteristics will also be presented for the ITT Population.

4.3.1 Demography

The following demographic characteristics will be analyzed:

- Age (years): summary statistics, including mean, median, SD, minimum and maximum, percentage, and number in each age (at randomization) category (age categories < 18, 18–65, > 65, used in the Development Safety Update Report)
- Sex: number and percentage of male and female patients
- Race: number and percentage of patients who are White, Black or African American, Asian (Indian Subcontinent, Other than Indian subcontinent), American Indian or Alaskan native, Native Hawaiian or other Pacific Islander, and Other
- Ethnicity: number and percentage of patients who are Hispanic or Latino and not Hispanic or Latino
- Weight (kg): summary statistics, including mean, median, SD, minimum, and maximum
- Body mass index (calculated from weight and height): summary statistics, including mean, median, SD, minimum, and maximum

Listings will be provided for demography and for randomization information.

4.3.2 Multiple Sclerosis Disease History

The following MS disease history characteristics will be analyzed:

- Duration since MS-symptom onset (years; i.e., divided by 365.25): summary statistics, including mean, median, SD, minimum, and maximum
- Duration since MS diagnosis (years; i.e., divided by 365.25): summary statistics calculated, including mean, median, SD, minimum, and maximum

Duration since MS symptom/diagnosis onset will be calculated up to the randomization date. If the month of symptom/diagnosis onset date is missing, the month of January will be used. If the day of symptom/diagnosis onset date is missing, the first of the month will be used.

- Type of MS diagnosed: number and percentage of patients with relapsing MS, secondary progressive MS with relapses (SPMS with relapses), secondary progressive MS without relapses (SPMS without relapses), progressive relapsing MS, and primary progressive MS

A listing of MS disease history will also be provided.

4.3.3 Previous and Concomitant Diseases Other than Multiple Sclerosis

The following previous and concomitant diseases other than MS will be analyzed:

- Previous diseases (other than MS) by System Organ Class (SOC) and Preferred Term (PT): number and percentage of patients with previous non-MS diseases, and number and percentage of patients with a history of each disease

- Concomitant diseases (other than MS) by SOC and PT: number and percentage of patients with concomitant non-MS diseases, and number and percentage of patients with each disease

A glossary listing of SOC terms, PTs, and verbatim terms for all diseases will also be provided.

4.3.4 Previous and Concomitant Treatments

Summaries of previous and concomitant treatments will be presented for the Safety Population only. The number of treatments and number and percentages of patients receiving treatments will be presented.

Treatments for MS

The following treatments for MS will be summarized:

- Previous treatments for MS by superclass term and PT
- IFN- β concomitant treatment allowed for MS during the ISP for patients in Group B
- Concomitant treatments for MS starting during the SFU Period following the ISP by PT for patients who did not enter the OOE
- Concomitant treatments for MS starting during the SFU Period following the OOE by PT

A listing of previous MS treatments by PT will be presented.

Other Treatments

The following other treatments will be analyzed:

- Previous treatments by superclass term and PT
- Previous procedures/surgeries by superclass term and PT
- Concomitant treatment present at baseline by superclass term and PT
- Procedures/surgeries present at baseline by superclass term and PT

A glossary listing of superclass terms, PTs, and verbatim terms for all medications and procedures will be provided. A glossary listing of grouping (procedures category), superclass terms, and PTs will also be provided.

4.3.5 Passive Immunization History and Vaccination History

The following information on passive immunization history and vaccination history will be analyzed:

- Passive immunization history: number and percentage of patients (yes or no) who have received the following passive immunizations: tetanus immunoglobulin, hepatitis B immunoglobulin, hepatitis A immunoglobulin, rabies antiserum, varicella zoster immunoglobulin, and other

- Vaccination history: number and percentage of patients (yes or no) who have received the following vaccinations: tetanus, pneumococcus polysaccharide, pneumococcal booster, diphtheria, influenza, KLH, varicella, measles, mumps, rubella, hepatitis B, hepatitis A, bacillus Calmette-Guerin, polio, pertussis, haemophilus influenza B, meningococcal, typhoid, yellow fever, smallpox, rotavirus, human papilloma virus, herpes zoster, and other. For tetanus, the number of years since prior tetanus vaccination will be summarized (summary statistics: mean, median, SD, minimum, and maximum).

Listings of passive immunization history and vaccination history will also be provided.

4.3.6 Expanded Disability Status Scale

The following characteristics of baseline Expanded Disability Status Scale (EDSS) (pre-dose) will be analyzed:

- Number and percentage of patients in each EDSS category (<4.0, and ≥4.0)
- Summary statistics, including mean, median, SD, minimum, and maximum

A listing of all EDSS assessments made during the whole study will be provided. Since an EDSS assessment should be performed if progressive multifocal leukoencephalopathy (PML) is suspected, this listing will include all available EDSS assessments, i.e., baseline and postbaseline.

4.3.7 Pre-Vaccination/Pre-Immunization Immunology Assessments

For the OC Population, the following pre-vaccination/pre-immunization immunology assessments will be summarized descriptively (note that, by design, some of these pre-vaccination/pre-immunization assessments are taken after baseline [Day 1]):

- Levels of anti-tetanus antibodies in patients measured prior to booster TT vaccine administration (prior to the start of ocrelizumab treatment)
- Levels of anti-pneumococcal antibody (µg/mL) against each of the 23 different serotypes (see Section 4.4.2.2) measured prior to administration of the 23-PPV vaccine
- Levels of anti-pneumococcal antibody (µg/mL) against each of the 23 different serotypes (see Section 4.4.2.2) measured 4 weeks after administration of the 23-PPV vaccine (which, for Group A1 patients, is prior to administration of the 13-PCV booster vaccine)
- Levels of anti-KLH antibody IgG measured immediately prior to first KLH administration (prior to the start of ocrelizumab treatment)
- In Groups A2 and B only, strain-specific GMTs measured immediately prior to immunization with the influenza vaccine (which can occur prior to or after the start of ocrelizumab treatment)

Each assessment listed above will be summarized descriptively by treatment group (as individually specified for each assessment) for the following summary statistics:

- Number and percentage of patients with values \leq lower limit of quantification (LLQ)
- Number and percentage of patients with values $>$ LLQ
- Geometric mean of known values $>$ LLQ
- 95% CI for geometric mean of known values $>$ LLQ, calculated using a normal approximation method on the log scale and then back-transformed to the original scale
- Geometric mean of all nonmissing values, imputing $\text{LLQ} \div 2$ for values \leq LLQ
- 95% CI for geometric mean of all nonmissing values, imputing $\text{LLQ} \div 2$ for values \leq LLQ, calculated using a normal approximation method on the log scale and then back-transformed to the original scale
- Median of known values $>$ LLQ
- Median of all nonmissing values, imputing $\text{LLQ} \div 2$ for values \leq LLQ

Pre-vaccination/pre-immunization assessments for the following exploratory immunology endpoints may be summarized descriptively using the same statistics listed above, depending on data availability at the time of the primary analysis:

- Overall levels of antibodies to the 23-PPV vaccine, i.e., IgG (using ELISA), measured prior to administration of the 23-PPV
- Overall levels of antibodies to the 23-PPV vaccine, i.e., IgM (using ELISA), measured prior to administration of the 23-PPV vaccine
- Levels of overall antibody response to the 13-PCV vaccine, i.e., IgG (using ELISA), measured 4 weeks after administration of the 23-PPV vaccine (which, for Group A1 patients, is prior to administration of the 13-PCV booster vaccine)
- Levels of overall antibody response to the 13-PCV vaccine, i.e., IgM (using ELISA), measured 4 weeks after administration of the 23-PPV vaccine (which, for Group A1 patients, is prior to administration of the 13-PCV booster vaccine)

